
14. Known intolerance (gastrointestinal, central nervous system symptoms) or hypersensitivity/drug allergy to opioids.15. Potential subjects taking monoamine oxidase inhibitors are excluded, as concomitant opiate use may increase the risk for serotonin syndrome.16. Potential subjects taking cyclosporin A are excluded unless they undergo a 6-week washout. Subjects are prohibited from using cyclosporin during the study. Please refer to Table-3 (including footnote 3) and Section 9.1.3.1.17. Potential subjects taking non-insulin biologics (including monoclonal antibodies), which modify the immune system, are excluded unless they undergo a 3-month washout. Please refer to Table-3 (including footnote 3) and Section 9.1.3.1.18. Prior Exclusion criterion 18 is not applicable to subjects enrolling under Protocol V6 and later.19. Exposure to any investigational medication, including placebo requires a 4-week washout (3 months for noninsulin biologics [e.g., monoclonal antibodies]). Please refer to Table-3 and Section 9.1.3.1.20. Potential subjects receiving UV-therapy (PUVA, UVA, UVB, Excimer) requires a 4-week washout. Subjects are prohibited from using UV-therapy for the duration of the study. Please refer to Table-3 and Section 9.1.3.1.21. Potential subjects who are taking opiates require a 14 –day washout. Subjects are prohibited from using opioids, including naltrexone, for the duration of the study. Please refer to Table-3 and Section 9.1.3.1.22. Potential subjects receiving gabapentin, pregabalin, calcineurin inhibitors, cannabinoid agonists, capsaicin, cryosurgery, topical doxepin, thalidomide or methotrexate, topical antihistamines, and topical corticosteroids require a 14-day washout. These medications are prohibited for the duration of the study. Use of systemic antihistamines are not permitted unless the subject has been on a stable dose for at least 4 weeks prior to screening and there are no plans to change the dose during the study. Please refer to Table-3 and Section 9.1.3.1.23. Potential subjects who have received systemic corticosteroids or local steroid injections of the PN lesions require a 4-week washout. These medications are prohibited for the duration of the study. Please refer to Table-3 and Section 9.1.3.1.24. Potential subjects are excluded if they have had any addition or discontinuation of their regularly used prescription drugs, or any changes in the doses of their regularly used prescription drugs in the 14 days prior to the screening period e-diary WI-NRS collection.25. Potential subjects taking central nervous system suppressants, such as barbiturates, benzodiazepines (with the exception of short-acting benzodiazepines specifically used on an intermittent and as needed basis), anxiolytics other than benzodiazepines, neuroleptics, and clonidine are excluded. These medications are prohibited for the duration of the study (see Section 10.6.2, footnotes 1 and 2 to Table-3 for definitions of ‘short-actingbenzodiazepines’).		

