- Case reports and small prospective datasets for several orally administered opiates used in chronic disease management have shown evidence for associated endocrine alterations in humans. In the US, these data have resulted in mandatory class labeling but this class warning does not appear in EU labeling at the current time. The US warning addresses: (1) the potential for serotonin syndrome when opiates are used concomitantly with certain antidepressants (this study excludes monoamine oxidase inhibitors); (2) rare cases of adrenal insufficiency; and (3) a risk for lowered sex hormone levels. For nalbuphine, standard animal toxicology studies did not show any signal for endocrine toxicity based on the gross and microscopic findings in endocrine organs. To date, no cases of serotonin syndrome have been observed, and no cases of adrenal insufficiency, or abnormal endocrine levels have been attributed to nalbuphine use in NAL ER studies.

Definitive data on NAL ER's effect on cardiac conduction is not yet available from a thorough QT study. In this setting, the ECG procedures and enrollment criteria are a standard precaution appropriate for long-term studies. In previous clinical efficacy studies conducted by the sponsor (TR02 and TR02EXT in UP, and TR03 and TR03EXT in PN), independent reviews of ECG data were performed by a blinded reviewer. These reviews found no evidence that nalbuphine meaningfully prolongs cardiac repolarization. Heart rate changes were overall small and did not suggest an effect by nalbuphine at any of the studied doses. The benign ECG observations from these prior clinical studies are supported by the preclinical in vitro study in the human ether-à-go-go-related gene assay, in which nalbuphine exhibited an inhibitory effect at concentrations that far exceed the nalbuphine plasma C_{max} by approximately 200-fold.

In summary, there are no nonclinical or clinical data suggesting that either of these endocrine and cardiac concerns is of specific relevance to NAL ER.

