6. Subjects using antidepressants must be on a stable dose for a minimum of 4 weeks prior to screening and must be willing to remain on their stable dose for the entire duration of the study.
7. Subjects who are human immunodeficiency virus (HIV) positive may enroll if they meet the following criteria: (a) currently on a stable (> 6 months stable use) and well tolerated highly active antiretroviral therapy regimen; (b) CD4 count > 500 cells/mL; and (c) HIV ribonucleic acid (RNA) < 50 copies/mL documented for at least 6 months prior to enrollment. If enrolled, these subjects should continue to have their CD4 and HIV RNA monitored by their HIV provider per their standard of care for the duration of the TR11 study, and the data should be reported and documented at the next study visit.
8. Females of childbearing potential must be using an acceptable method of birth control (if sexually active) for 14 days prior to randomization and throughout the study. All females of childbearing potential must have a negative pregnancy test at the screening and baseline visits.

For the purpose of this study, all females are considered to be of childbearing potential unless they are postmenopausal (i.e., at least 1 year since last menses and age > 50 years) or surgically sterile (i.e., tubal ligation, hysterectomy, and/or bilateral oophorectomy).

Sexually active female subjects of childbearing potential are required to use 1 barrier method (e.g., condom, cervical cap, or diaphragm) of contraception in addition to 1 other method (e.g., intrauterine device in place at least 1-month, stable hormonal contraception for at least 3 months, or Essure procedure, or spermicide).

Female subjects who are abstinent may participate in the study; however, they must be counseled on the requirement to use appropriate contraception should they become sexually active. This counseling should occur at each study visit and must be documented in source records.

9. Age 18 years and older at the time of consent, and a life expectancy of at least 18 months.
10. Willing and able to understand and provide written informed consent.
11. Willing and able to comply with study requirements and restrictions.
12. Agree to the confidential use and storage of all data and use of all anonymized data for publication including scientific publication.

9.5.2 *Exclusion Criteria*

Subjects meeting any of the following criteria must not be enrolled in the study:

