10.6.1 Concomitant Medications

Subjects may receive all clinically indicated medications during the study with the exceptions noted in [Section 10.6.2](#) and [Appendix 10](#).

Any medication taken by a subject within the 14 days prior to the screening period, and during the course of the study, will be recorded on the eCRF along with the reason for use. During the study, each subject will be instructed to report the use of all medication, including over-the-counter (OTC) medications, herbal medications, vitamins, and nutritional supplements on the study specific Subject Medication Log. Sites should instruct subjects to bring the log to each study visit for review (including referring to it during telephone contacts, as applicable). Subjects will also be instructed about the importance of not taking any new medications during the study (including OTC medications) without consulting the Investigator. After screening, if the subject begins taking prohibited or restricted medications, they are to be recorded on the corresponding Concomitant Medication eCRF (see [Section 10.6.3](#)).

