10.6.2 Prohibited Medications

Prohibited medications are summarized in [Table 3](#). Subjects receiving opiate drugs during the 14 days prior to the screening period are excluded from the study if unable to washout (see also [Section 9.1.3.1](#)).

Initiating use of opiate medications during the study should be done with caution with assessment of the subject for potential additive opiate AEs. If an enrolled subject requires daily treatment with opioid medications for greater than 7 days during the study, please contact the Medical Monitor. Use of acetaminophen, non-steroidal anti-inflammatory medications, and aspirin is permitted. If opioid medication is introduced in anticipation of chronic use, the subject is to be discontinued.

Concomitant use of opioid antagonists (e.g., naloxone, naltrexone) is also prohibited during the study, unless required for urgent reversal of opioid adverse effects or opioid overdose.

The following classes of drugs are prohibited during participation in this study due to the risk that they may cause increased respiratory depression, which could become life threatening with excess use:

- Central nervous system suppressants, such as barbiturates, benzodiazepines (with the exception of short-acting benzodiazepines specifically used on an intermittent and as needed basis), anxiolytics other than benzodiazepines, neuroleptics, and clonidine.

The phrase ‘short-acting benzodiazepines’ refers specifically to the following: triazolam, temazepam, brotizolam (available in EU only), zolpidem, and zaleplon. These drugs should be prescribed at the lowest effective doses and for the shortest period of time that is clinically

indicated during the conduct of the study. Subjects receiving these agents must be provided the patient information sheet as noted in [Table-1](#) and [Table-2](#) and in [Section 9.4](#).

Use of all other investigational products is prohibited during the study. A subject who initiates an investigational product during the study should be discontinued.

Subject are not to receive a medication that is classified as having a known risk for Torsade de Pointes (see [Appendix 10](#), for cardiovascular related prohibited medications with a known risk of Torsade de Pointes, classified as “KR”) unless the subject has been on a stable dose for at least 4 weeks prior to screening and there are no plans to change the dose during the study.

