Topical corticosteroids	Excluded within 14 days (e.g. 14-day washout) prior to the start of the screening e-diary WI-NRS collection	Prohibited (except topicals for limited 'Itch Intervention' as in Section 10.6.4)
Systemic corticosteroids	Excluded within 4 weeks (e.g. 4-week washout) prior to the start of the screening e-diary WI-NRS collection.	Prohibited
Topical capsaicin	Excluded within 14 days (e.g. 14-day washout) prior to the start of the screening e-diary WI-NRS collection	Prohibited (except for limited 'Itch Intervention' as in Section 10.6.4)
Anti-convulsant class drugs (e.g., gabapentin or pregabalin)	Excluded within 14 days (e.g. 14-day washout) prior to the start of the screening e-diary WI-NRS collection	Prohibited
Medications with anti-itch activity as documented in published literature even if this effect is not addressed in drug labelling or chronic itch guidelines.	Consult with the Medical Monitor for assessment of washout duration	Prohibited
Cannabinoid agonists	Excluded within 14 days (e.g. 14-day washout) prior to the start of the screening e-diary WI-NRS collection	Prohibited
Topical doxepin	Excluded within 14 days (e.g. 14-day washout) prior to the start of the screening e-diary WI-NRS collection	Prohibited (except for limited 'Itch Intervention' as in Section 10.6.4)
Thalidomide or methotrexate	Excluded within 14 days (e.g. 14-day washout) prior to the start of the screening e-diary WI-NRS collection	Prohibited
Cyclosporin A ³	Excluded within 6-weeks (e.g. 6-week washout) prior to the start of the screening e-diary WI-NRS collection	Prohibited

Table-3. Prohibited Medications and Washout Requirements		
Concomitant Medication	Study Entry (see Section 9.5)	During Study
Non-insulin biologics (including monoclonal antibodies) that modify the immune system ³	Excluded within 3-months (e.g. -month/12-week washout) prior to the start of the screening e-diary WI-NRS collection	Prohibited
Investigational drug products	Excluded within 4 weeks (e.g. 4-week washout) prior to the start of the screening e-diary WI-NRS collection Investigational monoclonal antibodies are excluded within 3months (e.g. 3-month/12-week washout) prior to the start of the screening e-diary WI-NRS collection ³	Prohibited
Cryosurgery	Excluded within 14 days (e.g. 14-day washout) prior to the start of the screening e-diary WI-NRS collection	Prohibited

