APPENDIX 9 CLASSIFICATION CRITERIA FOR CONGESTIVE HEART FAILURE

NYHA FUNCTIONAL CLASSIFICATION OF HEART FAILURE

Classification is based on functional limitations and severity.

Class Patient Symptoms

- I No limitation of physical activity. Ordinary physical activity does not cause undue fatigue, palpitation, dyspnea (shortness of breath).
- II Slight limitation of physical activity. Comfortable at rest. Ordinary physical activity results in fatigue, palpitation, dyspnea (shortness of breath).
- III Marked limitation of physical activity. Comfortable at rest. Less than ordinary activity causes fatigue, palpitation, or dyspnea.
- IV Unable to carry on any physical activity without discomfort. Symptoms of heart failure at rest.
If any physical activity is undertaken, discomfort increases.

¹ Adapted from Dolgin M, Association NYH, Fox AC, Gorlin R, Levin RI, New York Heart Association. Criteria Committee. *Nomenclature and criteria for diagnosis of diseases of the heart and great vessels*. 9th ed. Boston, MA: Lippincott Williams and Wilkins; March 1, 1994.

**APPENDIX 10 LIST OF DRUGS THAT PROLONG QT AND/OR CAUSE
TORSADES DE POINTES**

A list of drugs that prolong QT and/or cause Torsades de Pointes is available at www.crediblemeds.org. All concomitant medications taken by a subject should be verified on the Credible Meds website to confirm they DO NOT have a Known Risk (i.e. KR category) for Torsadede Pointes.

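### Monoamine oxidase inhibitors are barred at entry because of serotonin syndrome risk, but nothing in the protocol prohibits starting one during up to 52 weeks of dosing

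*Protocol*

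**What the plan says.** The protocol names MAOIs in three places. Exclusion criterion 15 appears in the synopsis and again in Section 9.5.2: "Potential subjects taking monoamine oxidase inhibitors are excluded, as concomitant opiate use may increase the risk for serotonin syndrome". Section 7.2.3, discussing the US opioid class warning, adds in parentheses that "this study excludes monoamine oxidase inhibitors".

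Section 10.6.1 sets the default once a subject is enrolled: "Subjects may receive all clinically indicated medications during the study with the exceptions noted in" Section 10.6.2 and Appendix 10. Section 10.6.2 opens by pointing to the table that serves as the working list: "Prohibited medications are summarized in" Table-3. Appendix 10 deals with a different hazard, Torsade de Pointes. It says concomitant drugs "should be verified on the Credible Meds website to confirm they DO NOT have a Known Risk (i.e. KR category").

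Two other provisions touch on new drugs. Under Section 10.6.1, subjects are told of the importance of "not taking any new medications during the study (including OTC medications) without consulting the Investigator". Under inclusion criterion 6, subjects already using antidepressants "must be willing to remain on their stable dose for the entire duration of the study".

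**The concern.** The reason given for criterion 15 is an interaction between two drugs taken together. That reason does not lapse at randomization; exposure to the opioid begins there. A rule that screens out current MAOI users and then says nothing about a subject who starts one in, say, Week 20 covers only the entry part of the risk it identifies.

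This is a patient-safety matter. When a subject or an outside prescriber asks whether a new drug is allowed, the Investigator will check Table-3. For MAOIs the table is silent, and the governing sentence in Section 10.6.1 makes silence mean permission. Protection then depends on the Investigator remembering an entry criterion.

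**Working it through.** The check is mainly textual: take each place where an on-study ban could sit and see whether it covers MAOIs.

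**Exceptions that Section 10.6.1 recognises**

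| Place | What it restricts on study | MAOIs named? |
|---|---|---|
| Section 10.6.2, text | Opioids, opioid antagonists, CNS suppressants (because of respiratory depression), other investigational products, drugs with known Torsade risk | No |
| Table-3 | The above, plus antihistamines, corticosteroids, immunomodulating and other anti-itch therapies, cannabinoids, cryosurgery and UV therapy; its catch-all row covers only drugs with documented anti-itch activity | No |
| Appendix 10 | Known Torsade risk only | No |

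**Discontinuation rules.** Sections 9.6 and 9.7 do not list starting an MAOI as a reason to stop treatment or leave the study. Section 9.7 does have a general best-interest ground.

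**How the other medication exclusions carry over**

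- Criteria 16, 20, 21, 22, 23 and 25 each state an on-study ban in their own text.
- Criteria 17 and 19 have no such sentence, but Table-3 supplies one. For criterion 17 it is the row "Non-insulin biologics (including monoclonal antibodies) that modify the immune system", marked prohibited during the study.
- Criterion 33 has an on-study condition in its own text and again in Section 10.6.2.
- Criterion 15 has no on-study sentence, no Table-3 row and no reference to Table-3.

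Criterion 24, on recent prescription changes, looks only at the 14 days before the screening diary collection, so it does not reach later starts. The pattern points to an omission rather than a choice.

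**Who could be affected.** Exclusion criterion 4 allows enrollment of subjects with stable general depression and, with Medical Monitor approval, of subjects whose isolated major depression was more than 3 years earlier. Inclusion criterion 6 binds only those already on an antidepressant. A subject who enters without one is not covered by it.

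**Duration and exposure.** Inputs: 14 double-blind weeks and 38 extension weeks (Section 9.1.1), and 360 subjects randomized 1:1, so 180 per arm.

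- Longest dosing: 14 + 38 = 52 weeks, which matches the synopsis.
- Arm 1 on active drug: 180 × 52 = 9,360 subject-weeks.
- Arm 2 on active drug: 180 × 38 = 6,840 subject-weeks.
- Total: 9,360 + 6,840 = 16,200 subject-weeks; 16,200 / 52 = 311.5 subject-years.

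This assumes that every subject completes, so it is an upper bound on the time during which the gap is open. It says nothing about how often an MAOI would be started.

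**The case against.** The strongest reply is that the protocol has already told Investigators the combination is unacceptable. Criterion 15 gives concomitant use as its reason, and the parenthesis in Section 7.2.3 speaks of the study, not only of entry. The exclusion has no washout route, which may partly explain its absence from a table built around washout periods. Several controls also stand in the way of harm: consultation before any new drug, review of the medication log at visits, the stable-dose rule for existing antidepressant users, exclusion of major psychiatric disorders, information on the signs of serotonin syndrome (Section 9.4), and the best-interest withdrawal ground in Section 9.7. Section 7.2.3 reports that no case of serotonin syndrome had been seen with NAL ER. The Amendment 6 rationale argues that nalbuphine has little interaction potential with antidepressants. The Investigator's Brochure, not available here, may also give guidance.

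Much of this stands as mitigation, and it is why the practical risk is probably small. It does not close the gap:

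- The Section 7.2.3 remark is background and is not among the exceptions that Section 10.6.1 recognises.
- Table-3 also holds safety rows (CNS suppressants, Torsade drugs), so its washout purpose does not account for the omission.
- Consultation works only if the Investigator has a rule to apply.
- Knowing the signs helps detect harm; it does not prevent co-administration.
- The Amendment 6 argument concerns sedating antidepressants, tricyclics, SSRIs and SNRIs. It does not address MAOIs, and criterion 15 was kept.

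It is also fair that the exposure total would be the same for any drug missing from the table. It describes how long the gap is open and does not by itself establish severity.

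**Conclusion.** The concern holds. The protocol identifies MAOI plus opioid as a serotonin syndrome risk, excludes current users for that reason, and then leaves MAOIs out of every list that governs medication use after entry. Read literally, Section 10.6.1 permits a clinically indicated MAOI for up to 52 weeks in Arm 1 and during 38 weeks of active treatment in Arm 2.

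The number of subjects affected cannot be estimated, because the documents contain no start rate and none is assumed here. It is probably low, and inclusion criterion 6 makes the group at risk smaller than 360. The conclusion rests on the protocol text alone; guidance in the Investigator's Brochure could soften the practical consequence but would not correct the protocol's own list. The primary endpoint, power and type I error are not touched. This is a correction that should be made on safety grounds.

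**What to change.** Add a Table-3 row for monoamine oxidase inhibitors, with the entry column reading *Excluded (exclusion criterion 15)* and the during-study column reading *Prohibited*. Add one sentence to criterion 15, in both the synopsis and Section 9.5.2: *MAOIs are prohibited for the duration of the study.*

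The cost is one table row and one sentence in two places, in a protocol amendment. Design, sample size and analysis stay as they are.

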6 LIST OF ABBREVIATIONS AND DEFINITION OF TERMS

AE	Adverse event
AESI	Adverse event of special interest
BMI	Body mass index
BID	Twice daily
CFR	Code of Federal Regulations
C _{max}	Maximum plasma concentration
CMH	Cochran-Mantel-Haenszel
CNS	Central nervous system
CRO	Clinical Research Organization
CTCAE	Common Terminology Criteria for Adverse Events
D	Day
DSMB	Data Safety Monitoring Board
ECG	Electrocardiogram
eCRF	Electronic case report form
EDC	Electronic data capture
e-diary	Electronic diary
ER	Extended release
EU	European Union
EudraCT	European Union Drug Regulatory Agency Clinical Trial FDA Food and Drug Administration
GCP	Good Clinical Practice
GI	Gastrointestinal
HCl	Hydrochloride
HCV	Hepatitis C virus

HD	Hemodialysis
HIV	Human immunodeficiency virus
ICF	Informed consent form
ICH	International Conference on Harmonisation
IEC	Independent Ethics Committee
IFSI	International Forum for the Study of Itch
IGA-PN	Investigator Global Assessment-Prurigo Nodularis
IgA-TTG	Immunoglobulin A tissue transglutaminase
IRB	Institutional Review Board
IND	Investigational New Drug
IV	Intravenous
IWRS	Interactive Web Response System
LFT	Liver function test
LLN	Lower limit of normal
MedDRA	Medical Dictionary for Regulatory Activities
MI	Multiple imputation
MITT	Modified intent-to-treat
NAL	Nalbuphine hydrochloride
n	number of available observations
NRS	Numerical Rating Scale
OTC	Over-the-counter
PAS	Prurigo Activity Score
PBI-P	Patient Benefit Index, pruritus version
PCC	Positive comparative control
PK	Pharmacokinetic

PK-PD	Pharmacokinetic-pharmacodynamic
PN	Prurigo Nodularis
PP	Per-protocol
PRO	Patient-reported outcome
RNA	ribonucleic acid
QD	Once daily
QoL	Quality of life
q4wk	every 4 weeks
q8wk	every 8 weeks
SAE	Serious adverse event
SAP	Statistical analysis plan
SHBG	Sex hormone binding globulin
SOWS	Subjective Opiate Withdrawal Scale
SubP	Substance-P
TEAE	Treatment-emergent adverse event
TSH	Thyroid stimulating hormone
ULN	Upper limit of normal
UP	Uremic Pruritus
US(A)	United States (of America)
UV	Ultraviolet
W	Week
WHO	World Health Organization
WI-NRS	Worst Itch Numerical Rating Scale
WOCBP	Woman of childbearing potential

